5.2 Exclusion Criteria

1. Prior radiation therapy within 2 weeks; or chemotherapy or non-cytotoxic therapy within 4 weeks or 5 drug half-lives, whichever is shorter (exception: 6 weeks for nitrosoureas or mitomycin C); or monoclonal antibodies within 4 weeks prior to the first dose of study treatment.
2. Concurrent use of any other investigational agent.
3. Known or clinically suspected central nervous system (CNS) or leptomeningeal metastases, unless irradiated or treated a minimum of 4 weeks prior to first study treatment and stable without requirement of corticosteroids for > 1 week.
4. Pregnant or breast feeding. A negative pregnancy test must be documented at baseline for women of childbearing potential. Patients may not breast-feed infants while on this study.
5. Significant cardiovascular disease or condition, including:
 - a. Congestive heart failure currently requiring therapy
 - b. Need for antiarrhythmic medical therapy for ventricular arrhythmia
 - c. Severe conduction disturbance
 - d. Angina pectoris requiring therapy
 - e. QTc interval > 450 msec (males) or > 470 msec (females) Fridericia's correction
Note: QTc values up to 500 ms will be acceptable where patient's medical history e.g., bundle branch block, is known to cause mild QTc prolongation and the condition is well controlled.
 - f. History of congenital long QT syndrome or congenital short QT syndrome
 - g. Uncontrolled hypertension (per the Investigator's discretion)
 - h. Class III or IV cardiovascular disease according to the New York Heart Association's Functional Criteria
 - i. Myocardial infarction within 6 months prior to first study drug administration
6. Known history of human immunodeficiency virus or active infection with hepatitis B virus or hepatitis C virus.
7. Known uncontrolled intercurrent illnesses, including uncontrolled viral influenza and COVID-19, systemic bacterial infections, and fungal infections.
8. Psychiatric disorder or altered mental status that would preclude understanding of the informed consent process and/or completion of the necessary studies.
9. Known allergic reactions to H1/H2 antagonists.

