AEs will be assessed per NCI CTCAE version 5.0. DLT is defined as any treatment related toxicity (i.e., not attributable to the underlying active disease or intercurrent illness) during the first 42 days (Cycle 1) of study treatment meeting any of the criteria below. Ongoing safety events beyond Cycle 1 will be reviewed across all cohorts during the study to help inform dose escalation decisions.

DLT includes:

1. Treatment-related hematological toxicities as follows:

- Grade 4 neutropenia.
- Any grade neutropenic fever.
- \geq Grade 3 thrombocytopenia lasting longer than 3 consecutive days.
- \geq Grade 3 thrombocytopenia with bleeding.
- Any other confirmed hematological toxicity \geq Grade 4 (a repeat test may be required for confirmation of an isolated abnormality in the absence of clinical signs, symptoms or other abnormal investigations, i.e., a suspected spurious value).

2. Treatment-related non-hematological toxicity \geq Grade 3 including:

- Electrolyte abnormalities that do not resolve within 48 hours of intervention (a repeat test may be required for confirmation of an isolated abnormality in the absence of clinical signs, symptoms or other abnormal investigations, i.e., a suspected spurious value).
- \geq Grade 3 infusion-related reactions.
- \geq Grade 3 cytokine release syndrome.
- Any hepatic toxicity meeting Hy's Law criteria.
- Grade 3 nausea/vomiting or diarrhea or other self-limited or medically controllable toxicities that last $>$ 72 hours regardless of medical intervention.

3. Any other treatment-related toxicity i.e., greater than at baseline, which is clinically significant and/or unacceptable, does not respond to supportive care and results in a disruption of the dosing schedule of more than 14 days.

4. Any death not clearly due to the underlying disease or extraneous causes.

DLT excludes:

- Alopecia of any grade.

Duration of treatment:

Upon completion of Cycle 1, in the absence of disease progression or unacceptable toxicity, patients may continue to be treated with NBF-006 at the same dose and schedule until disease progression, death, withdrawal of consent, Investigator decision to remove patient, or intolerable toxicity, whichever occurs first. A patient may continue on study (even if one or more criterion meets Disease Progression per RECIST 1.1) at the Investigator's discretion if deemed that the drug is well-tolerated and that the patient may continue to receive benefit from continuing treatment.

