Minimal changes in hematologic and clinical chemistries were observed in mice and monkeys in repeat-dose GLP toxicology studies. A common microscopic finding was the presence of vacuolation of the tubular epithelial cells or transitional epithelium, and aggregation of vacuolated phagocytic cells, in several organs (kidney, lung, urinary bladder, spleen and lymph nodes). Vacuolation was dose-dependent and showed signs of reversibility following the recovery period. Since the vacuolated phagocytic cells were observed in both NBF-005 and NBF-005 Empty (LNP only) treated animals, vacuolation was considered related to uptake and clearance of the LNP component. One of the NBF-006 LNP components is poly(ethylene glycol)-distearoylphosphatidylethanolamine (PEG-DSPE). Polyethylene glycol (PEG)-containing vacuoles in cells have been observed with several licensed PEGylated drugs with no associated pathological changes or human toxicity. There is evidence PEG vesicles can resolve with time.⁹ A review published in 2015 showed that PEG-related histologic changes, characterized as cellular vacuolation in certain tissues and cell types, is a common finding in nonclinical toxicology studies of PEGylated drugs. These changes were not associated with pathologic effects such as tissue degeneration, necrosis, and cellular distortion or changes in study endpoints including hematology, clinical chemistry, urinalysis, or organ weight.¹⁰ The body of evidence available for approved PEGylated biopharmaceuticals has not identified any clinically reported functional consequences for compounds where vacuolation was observed in toxicology studies.¹⁰

Mice were the most sensitive species. Deaths were observed at the 40 mg/kg/week in both the GLP-repeat dose toxicology study and the non-GLP study at this dose. In the GLP-repeat dose toxicology study, 11 out of 126 mice treated with 40 mg/kg/week of NBF-005 and 2 out of 30 animals treated with 40 mg/kg/week of the reference item (empty liposomes) were found dead or euthanized. In the non-GLP study, only one animal died and this was considered an incidental event due to the lack of pathologic findings. The dose of 20 mg/kg/week in mice was a non-toxic dose at which there were no deaths and no overt adverse findings.

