2.6 Potential Risks and Benefits

As this is the first-in-man study of NBF-006, no human data regarding the safety or potential benefit of NBF-006 was available before the study started. Since the clinical study began, 14 patients (IB v 4.0, 26MAR2021) have been treated at dose levels 1-4 (0.15 mg/kg, 0.3 mg/kg, 0.6 mg/kg, and 1.2 mg/kg) without any signs of overt toxicity. No clinically meaningful immune activation (complement and cytokines) was observed at dose levels 1-4 (0.15 mg/kg, 0.3 mg/kg, 0.6 mg/kg, and 1.2 mg/kg).

Nucleic acids like the siRNA are rapidly degraded by nucleases when not protected by LNPs. Much of the potential toxicity of NBF-006 would result from the LNP components

themselves. Many clinical studies of LNP-formulated siRNAs have observed dose-dependent inflammatory cytokine elevations.¹² Although many early phase trials of similar LNP-formulated siRNAs demonstrated a tolerable safety profile, immunogenicity (e.g., immune responses) could be a potential toxicity of this study treatment, especially at high doses or with frequent dosing of NBF-006.¹³

Based on other clinical trials with LNP-encapsulated siRNAs, the following are possible risks of NBF-006:

- Elevated cytokine levels or complement activation which could lead to inflammation. The symptoms would be flu-like symptoms, such as back pain, fever, nausea, headache, rash, rapid heartbeat, low blood pressure, temporary tightness in the chest, and trouble breathing. In severe cases, cytokine release syndrome could potentially develop.
- Allergic reaction (rash, wheezing, shortness of breath, heart palpitations, swelling of the face, and lowered blood pressure) to the drug or one of the drug or LNP components.
- In animals, NBF-006 administration led to increased vacuolation in tissues and cells. The appearance of vacuoles was not associated with any changes in organ function and went away over time.

Please see the current IB for further details about the potential risks and benefits associated with this study.

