4.4 Drug Product

NBF-006 is a sterile, injectable, parenteral product containing 10 mg of the active ingredient per vial. The vial is stored frozen at $-20\text{ }^{\circ}\text{C} \pm 5\text{ }^{\circ}\text{C}$ until use.

NBF-006 is an LNP formulation that incorporates five (5) key lipid components (i.e., Lp-081, cholesterol, dioleoyl phosphatidylethanolamine, dioleoyl phosphatidylcholine, and PEG-DSPE) to encapsulate siRNA API (NDT-05-1040), forming the siRNA LNP complex for drug delivery. The API, NDT-05-1040 siRNA, is a synthetic, double-stranded RNA. NBF-006 is reconstituted for use with 60 mM Acetate Diluent. The Acetate Diluent is provided with the drug product.

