6.0 TREATMENT OF SUBJECTS

6.1 Drug Preparation and Administration

NBF-006 is intended for intravenous (IV) infusion use and exposure to direct sunlight should be avoided. Before use, the drug product vial is reconstituted with 5.6 mL of Acetate Diluent to bring the total constituted volume to approximately 6.7 mL, yielding a drug concentration of approximately 1.5 mg/mL. The constituted suspension is diluted into sterile saline diluent to a total volume of 300 mL (or to a total volume of 320 mL for the 1.6 mg/kg dose level) in the clinic for IV infusion to patients. The admixture solution will achieve a final desired drug concentration within acceptable physiological pH and tonicity for IV administration to patients.

NBF-006 infusion will be implemented as a stepwise infusion:

- (1) 0.5 mL/min for 10 minutes,
- (2) then 1.5 mL/min for 10 minutes, and
- (3) finally 6 mL/min for the remaining volume

Total infusion duration of approximately 70 minutes (\pm 20 minutes).

Doses ranging from 0.15 to 1.6 mg/kg will be evaluated. The drug is administered weekly for 4 weeks followed by a 2-week rest period. The length of each cycle is 6 weeks.

For detailed instructions on vial concentration, preparation, and dispensing, please refer to the Pharmacy Manual.

The target infusion time is 70 minutes, but infusion rate will be adjusted as needed (e.g., due to infusion reaction). Premedication with H1/H2 antagonists should be considered if infusion reactions occur; refer to the management of infusion-related reactions (IRRs) outlined in Section [8.1.2.8](#).

The reconstituted drug (NBF-006 in Acetate Diluent) is stable in the glass vial for 2 hours at ambient conditions. The reconstituted drug solution is further diluted to the appropriate dose concentration with saline into a DEHP-free IV bag; this IV infusion solution is stable for 4 hours at ambient conditions. The drug product (lyophilized form, reconstituted solution, and IV infusion solution) should be kept out of direct sunlight.

Both NBF-006 and the Acetate Diluent will be provided by the Sponsor. Ordering instructions will be provided.

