8.1.2.8 Post-Infusion Observation Period

Observe/monitor for any signs and symptoms of IRRs, such as back pain, fever and/or shaking chills, flushing and/or itching, alterations in heart rate and blood pressure, dyspnea or chest discomfort, skin rashes, or anaphylaxis (e.g., generalized urticaria, angioedema, wheezing, hypotension, tachycardia, etc.).

During Part A of the study, each patient must remain in clinic for a minimum 6-hour safety observation period after each NBF-006 infusion until at least three patients at a specific dose level have been reviewed by the Safety Review Committee.

Reductions in the observation period at a given dose level may be recommended by the Safety Review Committee (consisting of Investigators, Theradex Oncology Medical Monitor, and Sponsor) after at least three patients have received a full cycle of treatment (defined as at least four doses and 2-week drug holiday) at that dose level.

Recommendations by the Safety Review Committee for a reduced observation period will be contingent upon:

- Absence of any significant safety concerns following a complete review of all clinical and laboratory data for all treated subjects at the given dose level and the preceding dose levels,
- Absence of any late-onset (>2 hours post-dose) IRRs or IRR symptoms that continue beyond 2 hours post-dose, and lack of any severe or serious IRRs,
- Review and consideration of cytokine and complement activation data at the given dose prior to making a recommendation to shorten the observation period.

If the Safety Review Committee recommends a reduced observation period, the minimum observation period allowed will be 2 hours following EOI from Cycle 2 onward during Part A of the study. Further reductions in the observation period may be suggested by the safety review committee as additional data has accumulated.

For Part B of the study, each patient must remain in clinic for a 6-hour safety observation period after the first dose, 2 hours after EOI for remaining doses in Cycle 1. The observation period may be further reduced to 30 minutes starting Cycle 2, after Medical Monitor and Investigator safety review. The observation period may be lengthened, if clinically indicated.

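### Allergy to a component of NBF-006 is a named risk, but the only allergy exclusion concerns H1/H2 antagonists, so a patient with a known component allergy is eligible as written (minor)

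*Protocol*

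**What the plan says.** **Eligibility.** Section 5.1 has twelve inclusion criteria and Section 5.2 nine exclusion criteria; the synopsis carries the same items. One exclusion concerns allergy, no. 9: "Known allergic reactions to H1/H2 antagonists". Section 4.8 requires patients to satisfy the eligibility requirements of Section 5.0 before registration.

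**Why H1/H2 antagonists appear.** They are the premedication named for infusion reactions. Section 6.1 states: "Premedication with H1/H2 antagonists should be considered if infusion reactions occur". Section 6.3 and Table 5 name the same drug classes.

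**The named risk.** Section 2.6 includes among the possible risks an allergic reaction "to the drug or one of the drug or LNP components".

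**The components.** Section 4.4 states: "NBF-006 is an LNP formulation that incorporates five (5) key lipid components". It lists them by name, ending with "dioleoyl phosphatidylethanolamine, dioleoyl phosphatidylcholine, and PEG-DSPE". The same section says that the product is reconstituted with an acetate diluent supplied with it.

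**Consequence of a severe reaction.** The DLT list in the synopsis includes "Grade 3 infusion-related reactions" and higher grades, and Section 6.1.3 has the same item. Section 8.1.2.8 counts anaphylaxis among the signs of an infusion-related reaction. Table 5 calls for permanent discontinuation at Grade 3/4. Under Section 5.4.2, a patient who stops in Cycle 1 for drug-related toxicity is not replaced.

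**The concern.** The protocol considered allergy when it set eligibility, but only allergy to the drugs used after a reaction. It did not carry the allergy risk it names for the product itself into the eligibility lists. A patient whose history records an allergy to a listed lipid or to the diluent can be registered and infused without breaching any criterion.

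What is at stake is mainly patient safety, because the foreseeable event includes anaphylaxis. There is a secondary effect on Part A. A severe reaction in Cycle 1 would enter the DLT count that decides whether 1.6 mg/kg is confirmed as safe, and that confirmation opens the four-patient cohort at this dose in Part B.

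**Working it through.** The protocol has no figure of its own to reproduce here. Section 9.6 says that no sample size calculation was made. The check is a reading of the provisions together, followed by an illustrative calculation.

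**1. Does any criterion cover the case?**
- Exclusion no. 9 covers H1/H2 antagonists only.
- The other eight exclusions concern prior therapy, other investigational agents, CNS disease, pregnancy and breast-feeding, cardiovascular disease, viral infection, uncontrolled intercurrent illness, and psychiatric disorder or altered mental status. None covers allergy.
- No inclusion criterion concerns allergy.
- Investigator discretion appears in Section 5.4, item 7, but that item governs stopping therapy, not entry.

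A known component allergy is therefore not a bar to entry in either list.

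**2. Does a later provision prevent the first exposure?** Section 6.1 has premedication considered once reactions occur, and Section 6.3 leaves antihistamine prophylaxis to the physician. The stepwise infusion and the 6-hour observation after the first dose may limit or detect a reaction. None of these stops the patient from receiving the product.

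**3. How would a reaction count?** If it is Grade 3 or higher, treatment-related and in Cycle 1, it is a DLT (Section 6.1.3). The patient stops (Table 5), is not replaced (Section 5.4.2) and stays in the DLT assessment. Section 6.1.1 ends escalation at 2 or more DLTs in 6.

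**4. How much could this move the 2-of-6 rule?** The documents give neither the share of patients with a known component allergy, *q*, nor the DLT rate in other patients, *p*. Both are assumptions here: *q* = 0.1% or 1%, and *p* = 5% or 10%. As an upper case, every allergic patient is taken to have a DLT.

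- Rate per patient: p′ = q + (1 − q)p
- P(2 or more of 6) = 1 − (1 − p′)⁶ − 6p′(1 − p′)⁵

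| p | q = 0 | q = 0.1% | q = 1% |
|---|---|---|---|
| 10% | 11.4% | 11.6% (p′ = 0.1009) | 13.2% (p′ = 0.109) |
| 5% | 3.3% | 3.4% (p′ = 0.05095) | 4.5% (p′ = 0.0595) |

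Example for p = 10%, q = 1%: 1 − 0.891⁶ − 6 × 0.109 × 0.891⁵ = 1 − 0.5003 − 0.3673 = 0.132.

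The change is about 0.1 to 1.8 percentage points over these assumptions.

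**The case against.** **The list contains no false statement.** Exclusion no. 9 is coherent, because it removes patients who cannot take the named premedication. Listing a possible risk in Section 2.6 does not promise a matching exclusion. This is fair: the point is a gap between two sections, not a wrong statement. It still stands as a cheap improvement, because the risk is the protocol's own and Section 5.0 is the entry standard.

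**The risk is partly mitigated.** Medical history is taken at screening, the infusion starts slowly, patients are observed, and the Safety Review Committee decides on escalation. An investigator may decline such a patient anyway. These measures reduce harm but do not make the patient ineligible. The Investigator's Brochure is not at hand and may contain a contraindication, but Section 4.8 ties registration to Section 5.0.

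**A reader might infer that the gap seriously distorts the Part A primary endpoint.** If one of six patients is taken to have a DLT for certain, the chance of at least one more among five is 1 − 0.9⁵ = 41% at p = 10%, against 11% without that assumption; at p = 5% it is 1 − 0.95⁵ = 23%, against 3%. The arithmetic is right, but it takes the DLT as given, and a DLT from any cause gives the same result. It leaves out how rarely such a patient would be screened, enrolled and react at Grade 3 or higher. Part B also uses the same exclusion list, so such a patient is not outside the population treated next. The documents do not support a claim of serious distortion.

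**A reader might also infer that allergy to any PEG-containing product must be excluded.** Section 2.3.4 discusses PEG in relation to vacuolation, not allergy. Cross-reactivity would have to come from outside the documents.

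**Conclusion.** The gap is confirmed on the text: the risk is named, the components are listed, and neither eligibility list excludes a patient known to be allergic to one of them. The consequence is an avoidable patient risk. The secondary consequence, limited to Part A Cycle 1, is that a severe reaction would add a DLT without replacement.

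The effect on the escalation decision cannot be quantified from the documents. It is probably small; the range of 0.1 to 1.8 points rests wholly on assumed allergy shares and DLT rates, with a reaction taken as certain. No reported decision has been affected: Section 2.4 records no DLT and one Grade 2 infusion reaction in the 14 patients at dose levels 1 to 4. Severity is minor.

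**What to change.** Reconcile Section 5.2 and the synopsis with Section 2.6 by adding one exclusion item for known hypersensitivity to the NBF-006 components named in Section 4.4 or to the acetate diluent. It can be assessed from the medical history already collected under Section 7.2, so no new test or visit is needed. The sponsor should set the clinical scope, for example whether an allergy to other PEG-containing products counts.

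The cost is one line in two places and a very small loss of eligible patients.

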5.3 Inclusion of Women, Minorities and Children

Both men and women and members of all races and ethnic groups are eligible for this study. Children are not eligible for this study because the safety and tolerability of the proposed dosing schedule has not been determined in adults.

5.4 Withdrawal Criteria

Protocol therapy will be discontinued at any time if any of the following situations occur:

1. Progressive disease (PD).
2. The development of toxicity which, in the Investigator's judgment, precludes further therapy.
3. Patient refusal.
4. Unacceptable AE(s).
5. Lost to follow-up/noncompliance.
6. Intercurrent illness that prevents further administration of treatment.
7. At the discretion of the Investigator.
8. Pregnancy.
9. Study termination.

Additionally, refer to the safety-related stopping rules in Section [8.1.2.11](#).

5.4.1 Withdrawn Subjects

When a patient is removed from the study, the Investigator will clearly document the reason in the medical record and complete the appropriate eCRF page describing the reason for discontinuation. In addition, every effort should be made to complete the appropriate assessments listed in Section [7.4](#).

5.4.2 Replacement of Subjects

Patients who discontinue due to toxicity (related to study drug) during Cycle 1, or who do not receive all doses due to toxicity in Cycle 1, will not be replaced. Patients who discontinue or who do not receive all doses for any reason other than toxicity will be replaced. Note, that all patients who enrolled in the study, regardless of their replacement, will be included in assessment of DLT per Section [6.1.3](#).

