6.1.2 Part B (Dose Expansion)

After MTD is confirmed in Part A for up to dose level 4 (1.2 mg/kg), enrollment in Part B may commence. Part B will enroll patients with previously treated progressive or metastatic NSCLC with confirmed KRAS mutation.

The two dose levels that will be explored further in Part B are 0.6 mg/kg and 1.2 mg/kg. Twenty patients will be enrolled in Part B, with 10 patients enrolled in each of the two cohorts. Both cohorts will be stratified for GSTT1-null genotype patients to ensure equal allocation to the cohorts with different doses. Once dose level 5 (1.6 mg/kg) has been confirmed to be safe in Part A, an additional 4 patients will be enrolled at dose level 1.6 mg/kg, for a planned total of 24 patients in Part B. This last dose level in Part B at 1.6 mg/kg will also be stratified for GSTT1-null genotype patients to be balanced with the previous two expansion cohorts as much as possible. The final proportion of GSTT1-null patients treated at the highest dose level may depend on the first 6 patients treated in Part A (not stratified).

Table 2: Part B NBF-006 Dose Levels

Dose level	NBF-006 dose	Number of patients
3	0.6 mg/kg	10
4	1.2 mg/kg	10
5	1.6 mg/kg	4*

*Dose level 5 pending confirmation of safety in Part A

NBF-006 will be administered by weekly infusion for 4 consecutive weeks of a 6-week cycle.

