6.2 Dose Interruptions/Withholding for Infusion Reactions or Other Reasons

Guidelines for management of IRRs, including circumstances for interrupting or

discontinuing dosing, are in Section 8.1.2.8.

Study drug may be withheld from a patient based on the Investigator's decision in the event of intercurrent illness, AEs, administrative reasons, or other reasons. If the patient's condition subsequently improves, or the situation that resulted in withholding study drug rectifies itself, the Investigator may resume dosing on the next practical dosing day.

Do not "make up" for missed or skipped doses i.e. if Week 3 dose is missed, do not administer a dose during the rest period (Week 5 or 6). Patients who miss a dose during Cycle 1 may be replaced per Section 5.4.2. The interruption and/or missed dose(s) should be recorded.

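### The non-toxicity replacement rule in Section 5.4.2 has no limit by part, cycle or reason, so Part B progressors must be replaced and unscanned early failures can be refilled out of sight

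*Protocol*

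**What the plan says.** Section 5.4.2 has three parts.

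- **Toxicity.** The patients not replaced are described as "Patients who discontinue due to toxicity (related to study drug) during Cycle 1, or who do not receive all doses due to toxicity in Cycle", where the cycle meant is again the first. This sentence is limited to Cycle 1.
- **Everything else.** "Patients who discontinue or who do not receive all doses for any reason other than toxicity will be replaced". No cycle, study part or reason is named, and replacement is mandatory.
- **Safeguard.** All enrolled patients, "regardless of their replacement, will be included in assessment of DLT per Section" 6.1.3. Response is not mentioned.

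Section 6.2 refers to the same rule differently: "Patients who miss a dose during Cycle 1 may be replaced per Section 5.4.2".

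Section 5.4 opens its list of withdrawal reasons with "Protocol therapy will be discontinued at any time if any of the following situations occur", and the first entry is progressive disease. Section 7.3 lets a patient who has completed at least three cycles omit one dose per cycle for convenience.

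On Part B size, Section 6.1.2 says "Twenty patients will be enrolled in Part B, with 10 patients enrolled in each of the two cohorts", and then "an additional 4 patients will be enrolled at dose level 1.6 mg/kg, for a planned total of 24 patients in Part B" once 1.6 mg/kg is confirmed safe in Part A. Section 9.2.1 makes best overall response a primary endpoint of Part B. Section 9.1 defines an Intent-to-Treat population (all enrolled, by signed consent) and an Efficacy Evaluable Population, which needs a baseline and at least one post-baseline assessment.

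**The concern.** In Part A the rule has a clear purpose: a patient who leaves Cycle 1 without toxicity tells us little about DLTs, so another is enrolled. In Part B efficacy is a primary objective, and stopping early for progression is itself an outcome, namely treatment failure.

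Progression is a reason other than toxicity, so a site following Section 5.4.2 literally would replace Part B progressors. Two things are at stake. One is operational: the cohorts have no defined end. The other is inferential: where an early failure has no post-baseline scan, it drops out of the efficacy set and its place is filled by another patient. The cohort can then again show 10 evaluable patients, weighted toward slower disease, with no visible sign of the loss. If early loss differs between doses, the dose comparison is affected too.

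**Working it through.** **1. The plan's own figure.** 10 + 10 = 20, and 10 + 10 + 4 = 24, which agrees with Section 6.1.2. Section 9.6 states that no sample size calculation was done, so there is no power figure to reproduce and no stated allowance for replacements.

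**2. The passages side by side.**

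| Place | Scope | Force |
|---|---|---|
| 5.4.2, non-toxicity sentence | any part, any cycle, any reason other than toxicity | mandatory |
| 6.2 | missed dose in Cycle 1 | optional |
| 7.3 | a convenience omission is permitted after three cycles | replacement not mentioned, but 5.4.2 as written would require it |

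Treatment continues until progression, death, withdrawal, investigator decision or toxicity (Section 4.5). With no time limit, almost every patient who does not stop for toxicity is eventually replaced, and so is the replacement. Enrolment then has no natural end.

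**3. Enrolment if a share q is replaced.** The documents give no q; 10%, 20% and 30% are assumptions. Replacements are taken to be lost at the same rate, so expected enrolment for n filled places is n/(1 − q).

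| q | per 10 places | per 24 places |
|---|---|---|
| 10% | 10/0.9 = 11.1 | 24/0.9 = 26.7 |
| 20% | 10/0.8 = 12.5 | 24/0.8 = 30.0 |
| 30% | 10/0.7 = 14.3 | 24/0.7 = 34.3 |

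**4. Effect on rates, replaced patients scanned.** They meet the Efficacy Evaluable definition and stay in the denominator. At q = 30% and a true disease control rate (DCR) of 40% among all dosed (assumed), 14.3 patients are enrolled and about 5.7 have disease control: 5.7/14.3 = 40%. There is no bias; only the number enrolled grows.

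**5. Effect on rates, early leavers unscanned.** They contribute no disease control and leave the denominator. The apparent rate is (true rate)/(1 − q).

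| q | DCR, true 40% | Response, true 10% (assumed) | Chance of ≥2 responders among 10 evaluable |
|---|---|---|---|
| 0 | 40% | 10% | 26.4% |
| 10% | 0.40/0.9 = 44% | 11.1% | 30.7% |
| 20% | 0.40/0.8 = 50% | 12.5% | 36.1% |
| 30% | 0.40/0.7 = 57% | 14.3% | 42.9% |

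The last column is 1 − (1 − r)^10 − 10r(1 − r)^9, with r the apparent response rate. These are upper bounds for each q, because they assume that none of the early leavers is scanned. If half are scanned at q = 20%, only 10% are lost and the DCR reads 0.40/0.9 = 44%, not 50%.

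**6. What replacement itself adds.** Without replacement, 10 dosed patients with 3 unscanned would be reported as 4/7 = 57%. With replacement, the expected figure is about 5.7/10 = 57%. The inflated rate is the same. The difference is that 7 evaluable of 10 shows the loss, and 10 evaluable hides it.

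**The case against.** A reader might infer that Section 5.4.2 by itself removes early progressors from the efficacy analysis, so that response is inflated whenever someone is replaced. The documents do not support that. No passage excludes replaced patients: the Intent-to-Treat population keeps everyone enrolled, and the Efficacy Evaluable Population keeps anyone with a post-baseline assessment. Section 7.4 lists a tumor measurement at End of Treatment for all who stop, and Section 5.4.1 asks for every effort to complete it.

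Timing narrows the problem further. The fourth dose is on Day 22 ± 3 and the first scheduled Part B scan is on Days 36–42. A patient whose progression is found on that scan has normally had all Cycle 1 doses and is evaluable. The mention of Cycle 1 in the adjoining sentence and in Section 6.2 suggests that a Cycle 1 rule was intended. Section 9.6 calls the Part B number approximate, and the analyses are descriptive. The loss of unscanned patients comes from the population definition, whoever is enrolled afterwards.

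Most of this stands, and it confines the bias to patients who decline or die before any post-baseline scan. Four points remain.

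- A Cycle 1 reading still does not exclude Part B.
- An approximate total does not accommodate a rule with no end point.
- The Intent-to-Treat set is defined by consent, dosed or not, so it is not an all-dosed response denominator; the statement on the primary evaluation of efficacy sits under the Efficacy Evaluable definition.
- Section 9.2.1 lists DLT among the Part B safety endpoints, but no Part B cohort size or decision rests on a DLT count, so DLT evaluability does not justify the rule there.

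Who is replaced is an enrolment instruction to sites, and an analysis plan cannot undo it later.

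**Conclusion.** The concern holds in a limited form. The text defect is certain: the mandatory non-toxicity sentence has no limit, cannot close at 10 + 10 + 4, and disagrees with Section 6.2 on both scope and force.

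The consequence for enrolment is about 26.7 to 34.3 patients instead of 24 if 10–30% of patients are replaced once, with replacements lost at the same rate; without a time limit there is no bound.

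The consequence for efficacy is conditional. Rates are unaffected for replaced patients who have a post-baseline scan. For those who leave unscanned, a true DCR of 40% would read at most 44%, 50% or 57% at losses of 10%, 20% or 30%. The loss shares and true rates are assumptions; the protocol gives none. Replacement does not create this inflation, but it conceals it by restoring the evaluable count. The matter should be corrected, but it does not show that the Part B result will be biased.

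**What to change.** Amend Section 5.4.2 and bring Sections 6.2 and 7.3 into line with it:

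1. Limit non-toxicity replacement to Cycle 1 DLT evaluability in Part A, use the same force (mandatory or optional) in both 5.4.2 and 6.2, and make clear that a dose omission permitted by 7.3 does not trigger replacement.
2. For Part B, state that a dosed patient who stops for progression, clinical deterioration or death is not replaced and stays in the cohort's response denominator as a non-responder. Limiting replacement alone would not be enough, because the unscanned patient would still fall outside the Efficacy Evaluable Population.
3. If dosed Part B patients may be replaced for logistical reasons, for example to complete PK or GSTP knockdown sampling, say so, and state that the replaced patient remains in the efficacy denominator. A rule that only never-dosed patients can be replaced is not needed.

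The cost is a short amendment. Enrolment does not grow and may fall. Reported response and disease control may be slightly less favourable.
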